5.6 Insurance

There is a business liability insurance with Baloise Insurance for Thim van der Laan AG in Landquart, where the investigation is carried out.

6 FURTHER ASPECTS

6.1 Overall ethical considerations

The study is carried out on healthy volunteers. Participants can opt out of the investigation at any time without consequences, as indicated in the informed consent form. The sample of healthy participants between the ages of 18 and 30 reflects a population that engages in regular physical activity, so the results are transferable to the general population. To prioritize the safety of participants, vulnerable populations such as pregnant women and those with certain health conditions were excluded to minimize possible adverse reactions. The results of this research can provide valuable insights into the mechanisms and application of recovery strategies after exercise. The use of a randomized controlled trial design is scientifically rigorous and minimizes bias. By considering covariates (e.g., gender) in randomization, the study increases internal validity and reduces the potential for confounding variables. The informed consent form explicitly states that participants will be informed of personal findings and random results relevant to their health (e.g. abnormal blood values).

6.2 Risk-benefit assessment

There are no health risks associated with participation in this examination. The CE-certified cold packs used in this study (Axanova Cold Hot Pearls Maxi Pack, Axanova AG) have been specially developed to exert a safe cooling effect on the affected muscle tissue. The product is used according to the instructions for use. As stated in the declaration of consent, the instructions for use of the CE-certified cold packs (Axanova Cold Hot Pearls Maxi Pack, Axanova AG) refer to the possibility of overcooling and the subsequent development of local frostbite due to local cold application. Through explicit instructions on use, duration, and frequency, the protocol helps

ensure that participants use the ice packs correctly, minimizing the risk of adverse effects and optimizing the intended appropriate cooling effect on muscle tissue.

As stated in the informed consent form, participants must expect to fatigue and become sore muscles due to the physical exertion from the knee extensor protocol and the measurement of the maximum isometric contraction level associated with a medium to high intensity. However, these complaints are not considered a significant health risk. The study design aims to ensure a safe and controlled practice environment with minimal potential for injury.

Venous blood samples were taken from a cubital vein by a trained specialist. However, as stated in the consent form for blood collection, there is a possibility that bruising, bleeding or swelling may occur at the injection site.

Participation in the study does not bring any direct benefit to the participants. While there is no direct personal benefit, participation in this research has the potential to provide valuable data for the scientific community. The results could benefit future athletes, people who engage in physical activity, and patients by shedding light on the best practices for post-exercise recovery.

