The thermal perception of the participants is recorded immediately after exposure to cold using the standardized Thermal Perception Scale (-4 to +4). This scale ranges from -4 ("extremely cold") to +4 ("extremely warm"), with 0 being considered neutral. The evaluation is carried out as a subjective self-assessment in order to document the individual temperature perception. Participants will be informed about the scale in advance. Since this is a purely subjective assessment, there is no risk for the participants.

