2.4 Investigation intervention

The repeated cold applications are carried out by the test subjects independently at home. For this, the test subjects receive 6 cold packs to take home (CE-certified Axanova Cold Hot Pearls Maxi Pack, Axanova AG). One cold pack is applied per thigh (2 packs per cooling session). The packs must be placed in a chest freezer/freezer compartment 1 hour before use. After the minimum cooling time has expired, the cold packs are placed on the thighs for 20 minutes with the fleece side down (skin contact). There must be at least 4 hours between cold applications. The cold packs may only be applied to the skin, without any additional pressure. The 20-minute cold application is described by the manufacturer Axanova as follows. We do not change the duration of application or form. The applications 24, 48 and 72 hours after the muscle soreness protocol are carried out by the test subjects at home and documented with a photo. Study participants upload these images directly to a designated cloud-based folder via a secure, password-protected link. This ensures that the data is transmitted and stored in encrypted form. When the intervention is carried out in the laboratory by the study staff, the temperature of each

cold pack is checked using an infrared thermometer to document possible temperature differences. This measurement is used to record potential variations in the cooling effect without influencing the application of the cold pack.

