5.2.1 Foreseeable adverse events and anticipated adverse device effects

Predictable AEs during the application of the MD.

Type of event	Description	Mitigation or Treatment Measures	Probable incidence
Skin irritation or redness	Localized erythema or irritation at the application site due to pressure or cold.	use protective materials; apply soothing creams or gels if necessary.	Medium
Pain or discomfort	Temporary pain or discomfort during or after application due to refrigeration.	Ask participants to report pain.	Small
Decreased local sensitivity	Temporary numbness or decreased sensitivity due to exposure to cold.	inform participants about this possibility; Avoid prolonged use to prevent complications.	Medium
Slight swelling or edema	Localized swelling due to prolonged cooling or improper use.	Monitor application time; elevate the affected area; Reduce application time for subsequent applications.	Small

No SAEs are expected.

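### Section 6.2 cites a frostbite warning, but frostbite is missing from the foreseeable-event table in 5.2.1 and no skin check or set adverse-event question is scheduled at the 24, 48 and 72 h visits

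*Combined protocol and SAP*

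**What the plan says.** **Risk statements.** Section 6.2 opens with "There are no health risks associated with participation in this examination". The same paragraph then says that the instructions for use "refer to the possibility of overcooling and the subsequent development of local frostbite due to local cold application", and that the consent form states this. The table in section 5.2.1 has four rows: skin irritation or redness, pain or discomfort, decreased sensitivity, and slight swelling. The sensitivity row reads "Temporary numbness or decreased sensitivity due to exposure to cold" and is rated Medium. The pain row is rated Small. Frostbite and overcooling have no row. Below the table stands "No SAEs are expected".

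**Detection.** Section 5.2 requires all AEs, serious AEs (SAEs) and device defects to be recorded from consent to the last procedure, with a safety follow-up phase of unstated length. Section 3.3 lists four items for each follow-up visit: blood markers, ultrasound of the muscle, soreness and maximum isometric contraction. The last paragraph of section 4.1 tells the cooled groups to cancel a session and make contact for symptoms such as severe pain or discomfort caused by the cooling.

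**Place of cooling.** Section 2.4 puts the applications at 24, 48 and 72 h in the home, with an uploaded photo. The schedule in section 3.3 lists cooling of groups A and B beside each laboratory follow-up without giving a place. Pack temperature is checked only when staff apply the pack in the laboratory: "This measurement is used to record potential variations in the cooling effect without influencing the application of the cold pack". Skin temperature recording stops in all groups 20 minutes after the exercise protocol (Synopsis, investigation procedures).

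**The concern.** Frostbite is the most serious local cold injury that the protocol mentions, and most cooling takes place without staff present. The plan therefore depends on how such an injury would come to notice. The home alert uses pain or discomfort as its example symptom, yet the protocol itself expects reduced sensation from the cold. Participants come to the laboratory on each of the next three days, but no listed item asks staff to look at the skin or to put a set question about it.

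Two things are at stake. Early skin injury could pass unnoticed while a participant goes on with repeated cooling. And if AEs are found only by volunteered report or chance observation, the trial's tolerability statement will be weak, because an absence of reports could mean either no injury or no one looking.

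**Working it through.** There is no stated figure to reproduce. The check compares the sections and counts sessions.

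**1. Risk statements side by side.** The denial of health risks and the frostbite warning in 6.2 cannot both stand as written. Section 5.2.1 is the place for anticipated device effects and omits the effect that 6.2 cites.

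**2. Sessions planned.** Inputs: 15 subjects per arm (section 4.1); group A cools three times a day on Days 1 to 4, group B three times a day on Days 2 to 4 (cooling logs, section 2.3).
- Group A: 4 × 3 = 12 per subject; 15 × 12 = 180.
- Group B: 3 × 3 = 9 per subject; 15 × 9 = 135.
- Total: 180 + 135 = 315.

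**3. Sessions in the laboratory.**
- Reading of section 2.4: only group A's first session. 15 × 1 = 15; 15/315 = 4.8%. Group B: 0 of 135. The other 300 (95.2%) are at home.
- Reading of the section 3.3 schedule as one laboratory session per follow-up visit: group A 15 × (1 + 3) = 60, group B 15 × 3 = 45. Total 105; 105/315 = 33%.

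The schedule allots 30 minutes to each follow-up. A 20-minute session inside it would leave 30 − 20 = 10 minutes for four measurements. That favours the home reading but does not settle it.

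**4. Skin temperature.** Recording ends 20 minutes after exercise, and group B's cooling starts at 24 h. On either reading, skin temperature under cooling is available for 0 of 15 group B subjects.

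**5. What 30 cooled subjects could show.** The documents give no frostbite rate, so the per-subject risk p is an assumption. With complete detection, the chance of at least one case is 1 − (1 − p)^30:

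| Assumed p | Chance of at least one case in 30 |
|---|---|
| 1% | 26.0% |
| 2% | 45.5% |
| 5% | 78.5% |
| 10% | 95.8% |

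If no case is seen in 30, the one-sided 95% upper bound is 1 − 0.05^(1/30) = 9.5%; for one arm of 15 it is 1 − 0.05^(1/15) = 18.1%. These bounds assume that every case is found. Incomplete detection makes them too optimistic.

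**The case against.** The strongest reply is that monitoring exists. Section 5.2 captures all AEs and device defects in every arm, so frostbite would be recordable although unlisted. Staff scan the ventral thigh, where the packs are applied, at each visit. Home sessions are photographed, and section 8 has the monitor verify AE documentation. Circulatory disorders, cold allergy and non-intact skin are exclusions, and the Synopsis adds disturbed thigh sensation. The symptoms in the home alert are examples, not a closed list. All of this stands, and a reader who inferred that the risk is effectively unmonitored would go beyond the documents. What remains is that none of these is a scheduled check: the ultrasound measures muscle thickness, and no one is assigned to review the photos for skin injury.

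Other stronger readings also fail:
- That group B is never observed while cooled. This holds on section 2.4 but not necessarily on the section 3.3 schedule, and photos give indirect observation.
- That pack temperature is barred from affecting use. The clause in 2.4 may only mean that measuring does not disturb the application. The text shows only that no action or reviewer is attached to the reading.
- That AEs are sought unequally between arms. Section 5.2 covers everyone, and the alert concerns symptoms of cooling, which controls do not receive.
- That expecting no SAEs contradicts the warning. Frostbite is an SAE only if it meets the criteria in section 5.1.

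Whether the secondary endpoints can show comparable cooling in group B is a separate question of treatment fidelity.

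**Conclusion.** The point holds as a gap in consistency and in planned detection; it is not evidence that participants are being harmed. Section 6.2 contradicts itself and does not match 5.2.1. No skin inspection or fixed AE question is scheduled at the three follow-up visits, and the example symptom in the home alert is one that the expected numbness could dull. Between 67% and 95% of planned sessions are outside the laboratory, depending on how sections 2.4 and 3.3 are reconciled (210 or 300 of 315).

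These counts assume 15 subjects per arm, full adherence to the cooling logs and no dropout. They measure supervision, not risk. The change is worth making before recruitment because it is cheap, but it does not bear on the validity of the primary comparison.

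**What to change.** 1. At the existing 24, 48 and 72 h visits, inspect both thighs and ask the same fixed AE questions (for example numbness, blistering, colour change, pain) in all three arms, recorded on the CRF. Using one question set in every arm makes the AE comparison interpretable.
2. Add overcooling and frostbite to the table in 5.2.1 and correct the no-risk statement in 6.2, so that the two sections agree.
3. Reconcile sections 2.4 and 3.3 on where the 24, 48 and 72 h cooling takes place. Clarify what the clause on not influencing the application means, and who reviews the pack readings.

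**Cost.** 45 subjects × 3 visits = 135 checks. At an assumed 2 minutes each, that is 270 minutes (4.5 hours) of staff time over the trial; each further minute per check adds 135 minutes. No new visits or staff are needed. The downside is a slightly longer visit against the 30 minutes planned.

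**Limit.** Exercise is in the morning, and Day 4 has three sessions at least 4 hours apart, so some cooling probably follows the 72 h visit. The length of the safety follow-up phase in 5.2 should therefore be stated.

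No cooling schedule, temperature threshold or stopping rule is proposed.

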7. QUALITY CONTROL AND DATA PROTECTION

7.1 Quality measures

Monitoring is carried out by [name]. [name] from the institution THIM - The International University of Physiotherapy, [name].

In her function as a monitor of the examination, [name] ensures that the examination is carried out and documented correctly. A detailed description of her activities as a monitor is listed below in point 9. This ensures that [name]. [name] is independent of the study team and is not employed by the examiner of the study.

For quality assurance, the sponsor, the ethics committee or an independent study monitor can visit the research facilities. On such occasions, direct access to the source data and all study-related files is granted. All parties involved treat the subject data in the strictest confidence.

7.2 Data recording and source data

The answers to the checklist, demographic and anthropometric data (gender, age, height, weight, estimated lower body fat percentage), room conditions (temperature, relative humidity), muscle soreness, and maximum isometric contraction force are manually recorded in the CRF. The data is then transferred in Microsoft Excel to the research computer of the research laboratory. Activation of the "Track Changes" option is ensured in the Excel file to ensure data protection and security. In addition, the Excel file is password-protected and backups are carried out regularly after measurements.

The study participants who run and document the application at home upload the images directly to a dedicated folder on Microsoft OneDrive for Business via a secure, password-protected link. It uses Azure Information Protection (AIP) to ensure secure transmission (with TLS/SSL encryption) and secure storage of data. The uploaded images are only accessible to authorized members of the study team, and storage is done in accordance with applicable data protection regulations. After the scan is completed or after the retention period has expired, the images are securely and completely deleted.

The blood sinking velocity is determined on site in the research laboratory using the Westergren method. The blood samples are then destroyed. The remaining parameters are determined by an external laboratory ([name], Buchs). After the blood is taken, the samples are picked up by a blood courier during the same day and taken to the medical laboratory, where the standardized analyses are performed. The creatine kinase values are determined by the ultraviolet method and the C-reactive protein values by the turbidimetric method. The blood samples are destroyed by the external laboratory and the reports are sent to us. We keep these reports confidential for a period of 10 years. The external laboratory only receives the numerical code of the participants (e.g. 001, 002, 003, etc.). No conclusions can be drawn from the external laboratory about the test subjects.

The images for the examination of muscle swelling are stored on an ultrasound machine. Only the numerical code is stored in the ultrasound machine and no personal data. It is not possible to draw conclusions about the test persons on the basis of the numerical code. The ultrasound machine is the property of the research laboratory and is operated only by research staff.

The key to the code is only with the principal investigator of this study. Only the study leader can decipher the code.

7.3 Confidentiality and coding

Study and participant data will be treated with the utmost discretion and will only be accessible to authorized personnel who need the data to perform their duties as part of the investigation. On the CRFs and other study-specific documents, participants are identified only by a numerical participant number. No personal data is presented or published. The signed declaration of consent and the completed checklist are kept in the original as a study document in a locked filing cabinet.

7.4 Retention and destruction of Investigation data and biological material

All study data will be archived for 20 years after the end of the study or premature termination of the examination. After this period, all data will be securely destroyed in accordance with the applicable data protection regulations and the guidelines of the study protocol. This applies to both the electronic data and all biological samples collected during the examination. The destruction is carried out in a secure way, for example by encrypting and completely deleting the electronic data and by physically destroying biological materials in order to exclude any possibility of reconstruction or identification of test subjects. If longer storage is necessary, for example for regulatory or scientific reasons, this will be coordinated in advance with the responsible ethics committees and authorities.

8 MONITORING AND REGISTRATION

The monitoring is carried out by [name] from the institution THIM - The International University of Physiotherapy, [name]. [name] ensures that the investigation is properly conducted and documented by performing the following activities, provided that they are relevant and necessary for the investigation:

- Verify that the investigator has and maintains adequate qualifications and resources throughout the duration of the study, that the facilities, including laboratories, equipment, and personnel, are suitable for the safe and proper conduct of the study and are maintained throughout the duration of the study.
- Review of study interventions
- Ensuring that the conditions for the interventions are acceptable.
- Verify that the study interventions are only made available to those subjects who are eligible.
- Ensuring that examinees are given the necessary instructions on the study interventions.
- Verify that the auditor is complying with the approved protocol and, if applicable, any approved changes.
- Verify that written informed consent has been obtained prior to each examinee's participation in the investigation.
- Ensuring that the auditor and the auditor's audit staff are adequately informed about the audit.
- Verify that the examiner is recruiting only eligible examinees.
- Reporting on the subject recruitment rate.
- Verify that the auditor provides all required reports, notifications, applications, and submissions, and that these documents are accurate, complete, timely, legible, dated, and identify the review.
- Verify that adverse events, concomitant medications and intercurrent diseases are reported according to the protocol on the CRFs.
- Ensuring that missed visits by the examinees, tests and examinations that were not carried out are clearly identified as such in the examination forms.
- All withdrawals and discontinuations of enrolled subjects from the study are reported and explained on the CRFs.

Source Data Verification (SDV) is also carried out as part of the monitoring to ensure the accuracy and integrity of the study data. This includes the following specific activities:

- Verification of sources and original data: It verifies that all data collected in the CRFs matches the original, primary data sources, such as participant data, lab reports, and notes from investigations.
- Control of study participants' documentation: Verify that all relevant demographic and medical data (e.g., age, gender, medical history, test results) are correctly captured and consistent with the original records.
- Verification of informed consent: Ensuring that each participant has written and informed consent prior to the start of the study.
- Adverse Event (AE) Review: Confirmation that all adverse events and concomitant medications are documented correctly and in accordance with the protocol.
- Control of study interventions: Verification that only eligible participants have received the study interventions and that all intervention data has been properly recorded.
- Examination of dropouts and non-perceptions: Verification that all abandonments from study visits and non-attendances have been properly noted and declared in the CRFs.

These measures ensure that the investigation meets the highest standards of data integrity and security, and that all recorded data is accurate and reliable.

9. FUNDING / PUBLICATION / DECLARATION OF INTEREST

This study is financed by Thim van der Laan AG in Landquart. The auditors are employed by this institute and are remunerated for their work on this study in accordance with their employment contracts. No further financial support is needed.

The sponsor shall enter and publish the summary of the study results in a public register in accordance with ClinO Art. 65a within one year of completion or termination of the investigation. An interruption of more than two years is considered to be an interruption of the investigation. For publication in the public register, the sponsor shall also ensure that an easy-to-understand summary of the study results is entered in BASEC within one year of completion or termination of the study. The entry is made at least in the national language of Switzerland in which the study participants were recruited.

